- a. If the subject’s primary study vaccine assignment is known at the time of consent for Study B1971033, the visits in Study B1971033 should be scheduled relative to the last dose of bivalent rLP2086 in the primary study. If the subject’s primary study vaccine assignment is blinded at the time of consent for Study B1971033, the visits in Study B1971033 should be scheduled relative to the last injection of investigational product in the primary study.
- b. Consent may be obtained at Visit 2 if subjects are enrolled at Visit 2.
- c. Vital signs will include blood pressure, pulse rate, and temperature (oral).
- d. Amount of blood collected is approximately 20 mL.

Abbreviations: AE = adverse event; hSBA = serum bactericidal assay using human complement; NDCMC = newly diagnosed chronic medical condition; RRI = research-related injury.

Table 2. Schedule of Activities – Booster Stage

Visit Identifier	Visit 7	Visit 8	Visit 9	Visit 10	Visit 11
	Booster Vaccination	Postvaccination Blood Draw 1	6-Month Telephone Contact	Postvaccination Blood Draw 2	Postvaccination Blood Draw 3
Visit Window	48 Months After Last Dose of Bivalent rLP2086 in Primary Study^a (1396-1484 Days After Last Dose of Bivalent rLP2086, and Within 42 Days After Visit 6)	1 Month After Booster (28-42 Days After Visit 7)	6 Months After Booster (168 to 196 Days After Visit 7)	12 Months After Booster (330-390 Days After Visit 7)	26 Months After Booster (750-810 Days After Visit 7)
Informed consent ^b	X				X
Review eligibility criteria ^c	X				X
Confirm continued eligibility ^c		X	X	X	
Vital signs ^d	X ^e	X		X	X
Medical history	X				
Physical examination	X				
Urine pregnancy test (all female subjects)	X				
Record any nonstudy vaccination and allergen immunotherapy ^f	X ^e	X	X	X	X
Blood sample ^g		X		X	X
IVRS/kit assignment	X				
Investigational product administration and observation	X				
Provide subject or parent/legal guardian with e-diary, caliper, measuring tape/ruler, and thermometer	X				
Record concomitant medications used to treat AEs	X	X	X	X	X
Review e-diary		X			

Table 2. Schedule of Activities – Booster Stage

Visit Identifier	Visit 7	Visit 8	Visit 9	Visit 10	Visit 11
	Booster Vaccination	Postvaccination Blood Draw 1	6-Month Telephone Contact	Postvaccination Blood Draw 2	Postvaccination Blood Draw 3

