Visit Window	48 Months After Last Dose of Bivalent rLP2086 in Primary Study^a (1396-1484 Days After Last Dose of Bivalent rLP2086, and Within 42 Days After Visit 6)	1 Month After Booster (28-42 Days After Visit 7)	6 Months After Booster (168 to 196 Days After Visit 7)	12 Months After Booster (330-390 Days After Visit 7)	26 Months After Booster (750-810 Days After Visit 7)
Collect e-diary		X			
Record use of antipyretic medication in the e-diary	Day 1 to 7				
Assess reactogenicity	Day 1 to 7				
Provide the subject with a memory aid		X			
Complete study visit/AE checklist	X	X	X	X	X
(S)AE collection appropriate for the visit ^h	X	X	X	X	X

- a. Visit 7 may occur a maximum of 42 days after Visit 6.
- b. If a subject reaches the age at which he or she is able to provide legal consent during the study, the subject’s consent must be obtained.
- c. Subjects must satisfy all eligibility criteria for Stage 1 and the booster stage. In addition, subjects participating in Visit 11 must meet eligibility criteria for Visit 11.
- d. Vital signs will include blood pressure, pulse rate, and temperature (oral).
- e. If Visits 6 and 7 do not occur on the same day, ensure that vital sign measurements and recording of nonstudy vaccinations are performed again at Visit 7.
- f. Nonstudy vaccination occurring from the final blood draw in the primary study until Visit 11. From Visit 7, this also includes allergen immunotherapy.
- g. Amount of blood collected is approximately 20 mL.
- h. Subject or subject’s parent(s)/legal guardian to report any AEs within 48 hours following Visit 10 and Visit 11.

Abbreviations: AE = adverse event; e-diary = electronic diary; IVRS = interactive voice response system; RRI = research-related injury; SAE = serious adverse event.

Table 3. Adverse Event Reporting Schedule

Stage 1							Booster Stage				
AE Type	Visit 1	Visit 2	Visit 3	Visit 4	Visit 5	Visit 6	Visit 7	Visit 8	Visit 9	Visit 10	Visit 11
SAE ^a	Nonactive reporting of SAEs to the primary study						From booster stage ICD to Visit 9			Nonactive reporting of SAEs to the B1971033 study	
NDCMC ^b	From 6-month telephone call in the primary study to Visit 11										
MAE							From booster stage ICD to Visit 9				
RRI ^c	48 Hours after blood draw	48 Hours after blood draw	48 Hours after blood draw	48 Hours after blood draw	48 Hours after blood draw	48 Hours after blood draw				48 Hours after blood draw	48 Hours after blood draw

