4.1.2. Booster Stage

4.1.2.1. Booster Stage Visits 7 to 10

1. Evidence of a personally signed and dated ICD indicating that the subject or subject's parent(s)/legal guardian has been informed of all pertinent aspects for Visits 7 to 10 of the booster stage of the study.
2. Subject continues to meet all Stage 1 inclusion and none of the Stage 1 exclusion criteria.

3. Subject is confirmed as having received bivalent rLP2086 in the primary vaccination study.
4. Subject has completed B1971033 Stage 1 and completed the Visit 6 blood draw.
5. Subject is available for the entire period of the booster stage and the subject or subject's parent(s)/legal guardian can be reached by telephone.
6. Healthy subject as determined by medical history, physical examination, and judgment of the investigator.
7. Male and female subjects of childbearing potential and at risk for pregnancy must agree to use a highly effective method of contraception through Visit 10 of the booster stage. A subject is of childbearing potential if, in the opinion of the investigator, he/she is biologically capable of having children and is sexually active. Refer to [Section 4.5](#) for further information.
8. Negative urine pregnancy test for all female subjects on the day of the booster dose.

4.1.2.2. Booster Stage Visit 11

1. For subject participating in Visit 11, evidence of a personally signed and dated ICD indicating that the subject or subject's parent(s)/legal guardian has been informed of all pertinent aspects of Visit 11.
2. Subject continues to meet all Stage 1 inclusion and none of the Stage 1 exclusion criteria.
3. Subject must have received 2 or 3 doses of bivalent rLP2086 in the primary study on a 0-, 2-, and 6-month or a 0- and 6-month schedule.
4. Subject must have completed booster vaccination at Visit 7.

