4.2.2. Booster Stage

1. Subjects who are scheduled to receive 1 or more doses of a human papillomavirus (HPV) vaccine as part of a 3-dose series during the 28 days after the booster vaccination.
2. A previous anaphylactic reaction to any vaccine or vaccine-related component.
3. Subjects receiving any allergen immunotherapy with a nonlicensed product or receiving allergen immunotherapy with a licensed product and are not on stable maintenance doses.
4. Bleeding diathesis or condition associated with prolonged bleeding time that would contraindicate intramuscular injection.
5. A known or suspected defect of the immune system that would prevent an immune response to the vaccine, such as subjects with congenital or acquired defects in B-cell function, those receiving chronic systemic (oral, intravenous, or intramuscular) corticosteroid therapy, or those receiving immunosuppressive therapy. Subjects in the United States with terminal complement deficiency are excluded from participation in this study. Please refer to the study reference manual (SRM) for additional details.
6. Significant neurological disorder or history of seizure (excluding simple febrile seizure).
7. Current chronic use of systemic antibiotics.

8. Current participation in another investigational study. Participation in purely observational studies is acceptable.
9. Received any investigational vaccines, drugs, or devices within 28 days before administration of the booster vaccination.
10. Any neuroinflammatory or autoimmune condition, including, but not limited to, transverse myelitis, uveitis, optic neuritis, and multiple sclerosis.
11. Pregnant female subjects, breastfeeding female subjects, male subjects with partners who are currently pregnant, or male and female subjects of childbearing potential who are unwilling or unable to use a highly effective method of contraception as outlined in this protocol through Visit 10 of the study.

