4.5. Lifestyle Guidelines

The following guidelines are relevant only to subjects who participate in the booster stage.

All male and female subjects who, in the opinion of the investigator, are biologically capable of having children and are sexually active must agree to use a highly effective method of contraception consistently and correctly through Visit 10 of the study (Month 12 after booster vaccination). Visit 11 (26 months after booster vaccination) is being added to the booster stage of this protocol amendment after subjects have completed Visit 10. Therefore, the contraception requirements do not apply to Visit 11.

The investigator or his/her designee, in consultation with the subject, will select the most appropriate method of contraception for the individual subject from the permitted list of contraception methods (see below), and instruct the subject in its consistent and correct use. Subjects need to affirm that they meet at least one of the selected methods of contraception. The investigator or his/her designee, at each study visit, will discuss with the subject the need to use highly effective contraception consistently and correctly according to the schedule of activities and document such conversation in the subject's chart. In addition, the investigator will instruct the subject to call immediately if the selected birth control method is discontinued or if pregnancy is known or suspected.

Highly effective methods of contraception are those that, alone or in combination, result in a failure rate of less than 1% per year when used consistently and correctly (ie, perfect use) and include the following:

- Established use of oral, injected, or implanted hormonal methods of contraception is allowed provided the subject plans to remain on the same treatment throughout the entire study and has been using that hormonal contraceptive for an adequate period of time to ensure effectiveness.
- Correctly placed copper-containing intrauterine device (IUD).
- Male condom or female condom used WITH a spermicide (ie, foam, gel, film, cream, or suppository). For countries where spermicide is not available or condom plus spermicide is not accepted as highly effective contraception, this option is not appropriate.
- Male sterilization with absence of sperm in the postvasectomy ejaculate.

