6.3.3. Visit 9 (168 to 196 Days after Visit 7), Safety Telephone Contact

Telephone contact should occur approximately 6 months after the booster vaccination; this contact should be attempted for all subjects who have received booster vaccination, including subjects who withdraw from the booster stage prior to Visit 9, unless they have withdrawn consent.

- Ensure that the subject continues to be eligible for the study and meets none of the withdrawal criteria ([Section 4](#)) and none of the temporary delay of blood draw criteria ([Section 4.4](#)).

- Complete the study visit/telephone contact checklist to:
 - Inquire whether the subject had any NDCMCs since the last visit as described in [Section 8](#) and the AE reporting schedule ([Table 3](#)).
 - Inquire about SAEs, NDCMCs, and AEs that resulted in evaluation at a medical facility since the last visit. Please refer to the SRM for additional details.
 - Inquire about neuroinflammatory and autoimmune conditions, such as transverse myelitis, uveitis, optic neuritis, and multiple sclerosis. Please refer to the SRM for additional details.
- Review AEs that were ongoing since the previous visit and record their end dates or confirm that they are still continuing.
- Report any SAEs to the sponsor as defined in [Section 8.7](#).
- Record AEs as described in the Safety section ([Section 7.2](#)) the Adverse Event Reporting section ([Section 8](#)), and the AE reporting schedule ([Table 3](#)).
- Record concomitant medications used to treat AEs as described in the Concomitant Treatment(s) section ([Section 5.7](#)).
- Record nonstudy vaccinations and allergen immunotherapy as described in the Concomitant Treatment(s) section ([Section 5.7](#)).
- Complete the source documents.
- Complete the CRFs.

6.3.4. Visit 10 (12 Months [330-390 Days] after Visit 7), Postvaccination Blood Draw 2

- Ensure that the subject continues to be eligible for the study ([Section 4](#)) and meets none of the temporary delay of blood draw criteria ([Section 4.4](#)).
- Collect vital sign measurements, including blood pressure, pulse rate, and temperature (oral).
- Record AEs as described in the Safety section ([Section 7.2](#)), the Adverse Event Reporting section ([Section 8](#)), and the AE reporting schedule ([Table 3](#)).
- Record NDCMCs as described in the Safety section ([Section 7.2](#)), the Adverse Event Reporting section ([Section 8](#)), and the AE reporting schedule ([Table 3](#)).

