6.5. Subject Withdrawal

The investigator and/or sponsor may withdraw a subject from the study if deemed appropriate at any time. Eligibility criteria as listed under Inclusion Criteria (refer to [Section 4.1](#)) and Exclusion Criteria (refer to [Section 4.2](#)) should be taken into consideration when determining if a subject must be withdrawn from the study.

Reasons why a subject may discontinue or be withdrawn from the study may include, but are not limited to, AEs (including any neuroinflammatory and autoimmune conditions, such as transverse myelitis, uveitis, optic neuritis, and multiple sclerosis), subject request, investigator request, death, discontinuation of the study by the sponsor, protocol violation, and being lost to follow-up. Subjects will not be replaced.

An effort must be made to determine why a subject fails to return for the necessary visits or is withdrawn from the study. Information detailing the circumstances leading to the withdrawal of a subject from the study, as well as the date of withdrawal, will be recorded on the study outcome CRF.

The decision to withdraw a subject from the study should be discussed with the sponsor. Every attempt must be made to collect all prompted reactogenicity data, AEs, or SAEs following each vaccination. Any AEs or SAEs that are continuing at the time of withdrawal from the study must be followed until the events have subsided, until values have returned to baseline, or, in case of permanent impairment, until the condition stabilizes.

When a subject discontinues or is withdrawn from the study, the investigator will notify the sponsor. When possible, the investigator will perform the procedures indicated for the next visit. If the subject has received the booster vaccination, but withdraws prior to Visit 9, provide the subject with a memory aid and complete the activities detailed for Visit 9.

Subjects may withdraw from the study at any time at their own request, or they may be withdrawn at any time at the discretion of the investigator or sponsor for safety or behavioral reasons, or the inability of the subject to comply with the protocol-required schedule of study visits or procedures at a given study site.

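### Table 2 footnote c carries the booster entry criteria forward to Visit 11, against Sections 4.1.2.2, 4.2, 4.5 and 6.3.5, and if followed it selects subjects on a primary safety outcome

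*Protocol*

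**What the plan says.** **Schedule.** In Protocol Table 2, eligibility criteria are reviewed at Visits 7 and 11 and continued eligibility is confirmed at Visits 8, 9 and 10. Both rows carry footnote c: "Subjects must satisfy all eligibility criteria for Stage 1 and the booster stage". The footnote goes on: "In addition, subjects participating in Visit 11 must meet eligibility criteria for Visit 11". Section 5 gives one dose, at Visit 7.

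**Booster-stage exclusions (Section 4.2.2).** Criterion 10 reads "Any neuroinflammatory or autoimmune condition, including, but not limited to, transverse myelitis, uveitis, optic neuritis, and multiple sclerosis". Criterion 5 covers immune defects and immunosuppressive therapy, criterion 6 significant neurological disorder or seizure, and criterion 11 includes pregnancy. None of these conditions is dated relative to the booster.

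**Other passages on the same question.**
- Section 4.2 presents the booster-stage exclusions as conditions for enrolling in that stage.
- Section 4.1.2.2 sets the Visit 11 criteria: consent, primary dosing schedule, booster received, and "Subject continues to meet all Stage 1 inclusion and none of the Stage 1 exclusion criteria". Section 6.3.5 tells sites to apply the Visit 11 criteria.
- Section 4.5 says "Therefore, the contraception requirements do not apply to Visit 11".
- Sections 6.3.2 to 6.3.4 repeat "Ensure that the subject continues to be eligible for the study". Sections 6.3.2 and 6.3.3 also point to withdrawal criteria in Section 4.
- Section 6.5 says the eligibility criteria "should be taken into consideration when determining if a subject must be withdrawn from the study".

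**Endpoints.** NDCMC percentages over Visits 7 to 11 and 8 to 11 are primary safety endpoints, restricted to subjects who go on to Visit 11 (Protocol 2.2.2 and 9.5; SAP 5.3 and Table 7, intervals 5 and 6).

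**The concern.** Entry criteria for a vaccination screen for fitness to receive the dose. Re-applied after the only dose, they screen on what has happened to the subject since. Here the screened conditions overlap with what the safety follow-up is looking for: Section 8.2 asks sites to watch for autoimmune and neuroinflammatory conditions throughout the booster stage, and such a condition, newly diagnosed, would ordinarily be an NDCMC.

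Two things are at stake. First, sites that read the footnote and sites that read Section 4.1.2.2 may keep different subjects at Visit 11. Second, where the footnote is followed, inclusion in a primary safety endpoint depends on not having had the event that the endpoint counts.

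**Working it through.** The plan states no figure on this point, so there is none to reproduce. The check is textual, followed by an illustration.

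**1. Does the footnote reach Visit 11?** Yes, as written. It is attached to the Visit 11 eligibility row, and the Visit 11 criteria come on top of the booster-stage criteria instead of replacing them. A new onset after Visit 7 meets exclusion 5, 6 or 10.

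**2. Do other passages agree?**

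| Subject's state at Visit 11 | Table 2 footnote c | Sections 4.1.2.2 and 6.3.5 |
|---|---|---|
| New autoimmune or neuroinflammatory condition | Not eligible (exclusion 10) | Not excluded by a booster criterion; Stage 1 exclusion 3 (severe condition, investigator's judgment) may apply |
| New seizure disorder | Not eligible (exclusion 6) | As above |
| New immune defect or immunosuppressive therapy | Not eligible (exclusion 5) | As above |
| Pregnant | Not eligible (exclusion 11) | Pregnancy not listed |

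The conflict with Section 4.5 is one of effect. The contraception clauses in 4.1.2.1 and 4.2.2 already end at Visit 10, but the pregnancy clause carries no end date. Under the footnote, a subject released from contraception after Visit 10 could be refused at Visit 11 for being pregnant.

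The withdrawal criteria cited at Visits 8 and 9 do not exist as a list in Section 4; withdrawal is covered in Section 6.5.

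**3. What happens to the case in the data?**
- *Visits 8 to 10.* Eligibility is checked at the same contact at which events are collected. An event recorded there stays in the booster-stage safety population and in the Visit 7–8, 8–10 and 7–10 NDCMC summaries. The loss is confined to later events and blood draws in subjects actually withdrawn.
- *Visit 11.* The visit windows are 330–390 and 750–810 days after Visit 7, so 750 − 390 = 360 to 810 − 330 = 480 days separate Visits 10 and 11. Active SAE reporting has ended at Visit 9 (Section 8.2), and Visit 11 is the only scheduled contact in that gap for collecting new chronic conditions. Section 6.3.5 lists the eligibility check before NDCMC recording. Even a case recorded by Visit 10 leaves the Visit 7–11 and 8–11 summaries if the subject is not entered at Visit 11.

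**4. Size.** Let n be the number who would attend Visit 11, k the number with such a condition, and m the number of those refused. The reported proportion is (k − m)/(n − m) instead of k/n. The shortfall is

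k/n − (k − m)/(n − m) = m(n − k) / [n(n − m)],

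which is positive whenever m > 0 and k < n. Protocol 3.4 gives n as up to 200. The documents give no incidence, so k and m are assumptions. Intervals are exact (Clopper-Pearson), the plan's own method (SAP 8.1.2); for zero events the upper limit is 1 − 0.025^(1/n).

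| k assumed | None refused | One refused | All refused |
|---|---|---|---|
| 1 | 1/200 = 0.50% (0.01–2.75) | 0/199, upper 1.84% | 0/199, upper 1.84% |
| 2 | 2/200 = 1.00% (0.12–3.57) | 1/199 = 0.50% (0.01–2.77) | 0/198, upper 1.85% |
| 3 | 3/200 = 1.50% (0.31–4.32) | 2/199 = 1.01% (0.12–3.58) | 0/197, upper 1.86% |
| 5 | 5/200 = 2.50% (0.82–5.74) | 4/199 = 2.01% (0.55–5.07) | 0/195, upper 1.87% |

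Worked for k = m = 2: the shortfall is 2 × 198 / (200 × 198) = 1.0 percentage point, and the upper limit for 0/198 is 1 − 0.025^(1/198) = 1.85%. With k = 5 and all refused, the reported upper limit (1.87%) lies below the proportion in the full group (2.50%).

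**The case against.** The strongest reply is that the footnote is an abbreviation in a table offered as an overview, and that the detailed text governs. In Section 6 the full Stage 1 and booster-stage list is checked only at Visit 7. Several booster criteria make sense only around vaccination, such as the same-day pregnancy test and the 28-day windows. Sections 4.1.2.2 and 6.3.5 set a Visit 11 list that omits the booster exclusions. On that reading no subject is refused for a new condition as such.

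A reader might go further than this point does and infer that affected subjects are barred from all follow-up after the booster, or that the 26-month endpoints cannot show these conditions. The documents do not support that. Withdrawal under Section 6.5 is a matter of judgment, even though that section names autoimmune and neuroinflammatory events among possible reasons. It asks for next-visit procedures where possible and for ongoing events to be followed. The 6-month call is attempted for every boosted subject who has not withdrawn consent, including those withdrawn from the stage. Section 8.2 has NDCMCs recorded through Visit 11, and SAP 8.2.4.2.3 lists neuroinflammatory and autoimmune events without a Visit 11 condition.

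This disposes of the strong reading for Visits 8 to 10. It does not settle Visit 11. The footnote's wording is mandatory and additive, and nothing says which passage prevails. The 6-month call cannot cover months 6 to 26. Visit 11 has its own consent, so refusing entry is not clearly a withdrawal that triggers Section 6.5. The SAP listing does not restore a case to the endpoint.

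**Conclusion.** The contradiction is established from the text and does not depend on any assumed number: footnote c and Sections 4.1.2.2, 4.2, 4.5 and 6.3.5 do not give one answer on who may enter Visit 11. The consequence is conditional. Where a site follows the footnote at Visit 11, the Visit 7–11 and 8–11 NDCMC proportions are biased toward zero for the conditions named in the booster exclusions. If every site did so, those conditions would be reported as zero among entered subjects. The 2/200 to 0/198 example rests on an assumed case count, on the upper planning figure of 200 and on both cases being refused. With partial adherence to the footnote the bias is smaller, as the middle column of the table shows.

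The study is descriptive, two NDCMC intervals are affected, and the immunogenicity endpoints are touched only through missing Visit 11 titers. Severity is moderate.

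**What to change.** Reconcile Table 2 footnote c with Sections 4.1.2.2, 4.2, 4.5, 6.3.2 to 6.3.5 and 6.5, so that the protocol has one rule on which criteria apply after Visit 7. In doing so:

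- Keep the Stage 1 criteria that 4.1.2.2 re-applies at Visit 11. A reader might infer that consent and fitness for a blood draw would be enough after Visit 7. That would drop the Stage 1 exclusions for recent blood products and for another serogroup B vaccine, both of which could affect titers.
- State what follows when a criterion is no longer met after the booster: whether it affects safety data collection, blood draws, or only membership of the evaluable population. SAP 5.2, item 1, requires all Stage 1 and booster-stage criteria without naming a visit and should be aligned. Whatever rule is chosen, inclusion in the 26-month NDCMC endpoints should not depend on the outcome.
- Replace the reference at Visits 8 and 9 to withdrawal criteria in Section 4 with one to a passage that exists.
- In the SAP, report how many boosted subjects were not entered at Visit 11 because of a new condition. Add a supporting Visit 7–11 NDCMC summary that counts these subjects, with their recorded events, in numerator and denominator.

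The cost is wording in a protocol and SAP amendment, one extra count and one supporting summary. No visit is added to the schedule. Section 4.5 says Visit 11 is being added after subjects have completed Visit 10, so the Visit 11 wording matters most.
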